# Modification

## Basic Info

Confirmation Number:	deeeecd
Protocol Number:	834878
Created By:	[name]
Principal Investigator:	[name]
Protocol Title:	Adaptation of the OurCareWishes.org advanced care platform for persons with dementia in nursing homes and caregivers
Short Title:	Our Care Wishes - Dementia
Protocol Description:	The research study is being conducted to develop an Our Care Wishes Dementia website. This website will help persons with dementia and their surrogate decision-makers document personal and medical care wishes.
Application Type:	EXEMPT Category 2

## PennERA Protocol Status

Acknowledged

### Resubmission\*

No

### Are you submitting a Modification to this protocol?\*

Yes

## Current Status of Study

### Study Status

Closed to subject enrollment (remains active)

*If study is currently in progress, please enter the following*

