### Number of subjects enrolled at Penn since the study was initiated

15

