### Actual enrollment at participating centers

7

*If study is closed to further enrollment, please enter the following*

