that their participation is completely voluntary and can be ended at any time. Each session will last up to half an hour. To evaluate the acceptability and usefulness of the platform, we will also recruit up to 15 Healthy Patterns Sleep Study participants (IRB protocol # 825000) for virtual beta testing of the website. Participants will be selected if they have previously agreed to being contacted for research and if they have a computer or smartphone on which to view the website and surveys. Participants will be recruited as dyads (caregiver and person with dementia). Dyads will consent to the study staff contacting them via phone or BlueJeans and guiding them through the website and accompanying Qualtrics surveys. Qualtrics surveys will be administered before and after the viewing of the website; surveys will ask dyads for their feedback on the website and their confidence making decisions about future care. Virtual beta testing platforms will depend on the participants' ability and resources, and may include telephone, Skype, FaceTime, or BlueJeans and any internet browsers. Study staff will take notes on the reactions of dyads in order to improve the website and user experience after beta testing. When filling out the surveys, no identifiable information will be collected. The calls and/or video chats will not be recorded. Each Healthy Patterns participant within each dyad will receive \$15 via Greenphire gift cards at the end of study participation. Gift cards will be mailed to dyads. Each session will last up to an hour. Some identifiable information (name, DOB, email address, phone number, address) will be entered in the website but will not be used or recorded in the study. The website is hosted by Pantheon, which is a Penn approved hosting platform. The site is encrypted with SSL (Secure Sockets Layer) to protect participant information. Aim 3: Randomized Pilot. Setting/sample. We will conduct the pilot study in up to four Genesis facilities with diverse locations (urban, suburban, rural). We will also include at least one facility that serves mostly minority populations to test the effectiveness of the OCW-Dementia module among racially and ethnically diverse PWD. We will recruit up to 50 patients/residents and their SDMs. Eligible PWD will be receiving short- or long-term care at a participating NH, have documented moderate to severe cognitive impairment and have an identified SDM. We will exclude residents clearly exhibiting terminal decline, thereby reducing the likelihood of attrition. Study team members will work with Genesis staff to recruit dyads (Genesis residents and their family members or supportive decision-makers (SDMs) who are interested in participating in the study. Study team will read an assent script to interested SDMs, gain verbal assent and then send SDMs the study summary and copy of the assent script. After verbal assent is acquired, dyads will be assigned to the intervention group or usual care arm. At each site, up to 10 dyads will be recruited. Half of the dyads recruited at each site will receive their usual care and complete the demographics survey, COVID-19 survey and pre and post confidence in decision making surveys. The second half of dyads recruited at each site will receive the intervention as well as complete the demographics survey, COVID-19 survey and pre and post confidence in decision making surveys.

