#### **Subjects enrolled by Penn Researchers**

50

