#### **Subjects enrolled by Collaborating Researchers**

0

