## **Subject recruitment**

For Aim 2, Genesis staff members recruited will be those recommended by Genesis management. Additional participants will be recruited from the Healthy Patterns Sleep Study (IRB Protocol 825000) who have agreed to be contacted for future research. These participants (dyads) are persons with dementia with caregivers in the greater Philadelphia area who will have access to a smartphone or computer. We will conduct the pilot study in up to four Genesis facilities with diverse locations (urban, suburban, rural). We will also include at least one facility that serves mostly minority populations to test the effectiveness of the OCW-Dementia module among racially and ethnically diverse PWD. We will recruit up to 50 patients/residents and their SDMs. Eligible PWD will be receiving short-or long-term care at a participating NH, have documented moderate to severe cognitive impairment and have an identified SDM. We will exclude residents clearly exhibiting terminal decline, thereby reducing the likelihood of attrition. Strategies to address potential study limitations. If we are unable to rapidly recruit sufficient numbers of PWD and SDMs at up to four facilities for Aim 3, we will work with Genesis leaders to expand recruitment to additional facilities. There are 25 Genesis facilities within a 25-mile radius of the Penns campus. For Aim 3, Study team members will work with Genesis staff to recruit dyads, ie. Genesis residents and their supportive decision-makers (SDMs) who are interested in participating in the study. Study team will read an assent script to interested SDMs, gain verbal assent and then send SDMs the study summary and copy of the assent script. After verbal assent is acquired, dyads will be randomized to the intervention group or usual care arm. At each site, up to 10 dyads will be recruited. Half of the dyads recruited at each site will receive their usual care and complete the demographics survey, COVID-19 survey and pre and post confidence in decision making surveys. The second half of dyads recruited at each site will receive the intervention as well as complete the demographics survey, COVID-19 survey and pre and post confidence in decision making surveys.

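### Enrolment is reported closed at no more than 22 subjects, but the Analysis Plan's only power figure is 91.5% for 25 per arm; the planned test then has at most 67.5% power

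*Combined protocol and SAP*

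**What the plan says.** Under Current Status of Study, the status is "Closed to subject enrollment (remains active". The fields that follow are "Number of subjects enrolled at Penn since the study was initiated", answered 15, and "Actual enrollment at participating centers", answered 7. A further field counts 4 subjects in therapy or intervention.

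Under Characteristics of the Study Population, "Subjects enrolled by Penn Researchers" is 50 and "Subjects enrolled by Collaborating Researchers" is 0. The Design and Subject recruitment sections set an upper limit of 50 residents with their decision-makers for the Aim 3 pilot, allocated half and half: "Half of the dyads recruited at each site will receive their usual care". If recruitment is slow, "we will work with Genesis leaders to expand recruitment to additional facilities".

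The Analysis Plan expects 30% ACP completion under usual care and 70% with the intervention. It gives 91.5% power with 25 per arm, for a one-sided pooled-variance Z-test at 0.05. It states no other sample size or power and plans no confidence interval. The Modification Summary covers personnel changes only.

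**The concern.** The comparison of ACP completion is framed as a hypothesis test, and the only power attached to it is above 90%. The same document reports that recruitment has ended well short of the size behind that figure. A reader who relies on the Analysis Plan would give a non-significant result more weight than the closed study can support. With no interval planned, nothing in the analysis would show how wide a range of effects remains compatible with the data.

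**Working it through.** **Inputs.** From the Analysis Plan: rates 0.30 and 0.70, one-sided alpha 0.05, pooled Z-test, 25 per arm. From Current Status of Study: 15, 7 and 4. From Subject recruitment: equal allocation within site.

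**Method.** With x completions among n_C usual-care dyads and y among n_I intervention dyads:

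z = (y/n_I − x/n_C) / √[p̄(1 − p̄)(1/n_I + 1/n_C)], where p̄ = (x + y)/(n_I + n_C).

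Power is the sum of Bin(x; n_C, 0.30) × Bin(y; n_I, 0.70) over all (x, y) with z ≥ 1.645.

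**Step 1: reproduce the plan.** At 25 versus 25 the sum is 0.915, which matches the stated 91.5%. The normal approximation is close: null SE = √(0.25 × 2/25) = 0.1414, alternative SE = √(0.21 × 2/25) = 0.1296, and Φ[(0.40 − 1.645 × 0.1414)/0.1296] = 0.902. The design figure is sound.

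**Step 2: the most favourable reading of the counts.** 15 + 7 = 22. This assumes that the two counts do not overlap, that each subject stands for one dyad, and that all were randomised in Aim 3. The enumeration was run over every split of 22 or fewer dyads.

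| Arms | Basis | Power | Missed |
|---|---|---|---|
| 25 vs 25 | Design | 91.5% | 8.5% |
| 12 vs 10 | Highest of all splits of 22 or fewer | 67.5% | 32.5% |
| 11 vs 11 | Equal split of 22 | 67.1% | 32.9% |
| 9 vs 6 | Highest if the total is 15 | 52.4% | 47.6% |
| 4 vs 18 | If the 4 is the whole intervention arm | 47.5% | 52.5% |

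For scale, equal arms first pass 80% at 17 per arm (80.7%; 16 per arm gives 77.2%). That is 34 dyads, 34 − 22 = 12 more than the most favourable reading.

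**Step 3: how generous the ceiling is.** With both rates at 30%, the test's actual one-sided type I error at 12/10 and 10/12 is about 6.6% to 7.3%, above the nominal 5%. By the normal approximation, 11 versus 11 gives null SE = √(0.25 × 2/11) = 0.2132, alternative SE = √(0.21 × 2/11) = 0.1954, and Φ[(0.40 − 1.645 × 0.2132)/0.1954] = 0.600.

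**Step 4: why the actual figure cannot be read off.**
- The 7 may lie within the 15, since the plan foresaw 0 subjects enrolled by collaborators.
- The counts may be persons: the Consent section names both the person with dementia and the decision-maker as participants. Then 22 persons are 22/2 = 11 dyads.
- Aim 2 testers may be included. The Design section says that "we will also recruit up to 15 Healthy Patterns Sleep Study participants", the same number as the Penn count.
- The 4 may be a current or a cumulative count, and the field names no aim.

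**Step 5: no floor.** Power does not fall steadily with size when arms are this small. It is 25.5% at 4 versus 4 but 42.0% at 3 versus 3, and 24.0% at 2 versus 2. A few chosen scenarios therefore do not bound power from below.

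**The case against.** The strongest reply is that nothing in the Analysis Plan is false. The power statement is conditional on enrolling 25 per arm, and it is correct on that condition. The 50 is an upper limit in Design and Subject recruitment, so a smaller number does not breach it. The counts are administrative fields in a submission about personnel. Under-recruitment is a matter of conduct, and the study is called a pilot. All of this stands. A reader might infer that the 91.5% was miscalculated or that the recruitment limit was violated; the documents support neither.

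A reader might also infer that 22 dyads were randomised, or that the closed study's power lies in some definite range. Neither follows. The 22 is a best case, and only the ceiling is a bound. That ceiling also depends on the method: a one-sided Fisher test at 11 versus 11 would have 49.5% power.

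Nor does any section say that a non-significant result would be read as no effect. That is a risk left open by the plan, not something it states.

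Power computed after the event is often uninformative, but that criticism applies to power based on the observed effect. Here the pre-specified 70% and 30% are kept and only the arm sizes change. What survives the reply is that the plan's only size and power statement describes a study that, by its own status fields, will not exist.

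**Conclusion.** The point holds as a failure to update, not as an error in the design calculation. On the most favourable reading of the counts, the planned test has at most 67.5% power for 70% versus 30%. It therefore misses a true effect of that size at least 32.5% of the time, nearly four times the design figure (32.5/8.5 = 3.8). The ceiling needs no assumption about how the arms split. It does rest on the plan's own rates and test, and it is generous because the test exceeds its nominal level at the splits that attain it. Every other reading of the 15 and the 7 gives fewer randomised dyads, so the ceiling stands under all of them. The 47.5% at 4 versus 18 holds only if the 4 is the full intervention arm, which is an assumption. No lower limit on power can be given.

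**What to change.** In the Analysis Plan:

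1. State the number of randomised Aim 3 dyads per arm, separate from Aim 2 participants, and reconcile it with the 15, 7 and 4 under Current Status of Study.
2. Label 91.5% as the original design figure for 25 per arm, and restate power for 70% versus 30% at the achieved arm sizes.
3. Keep the pre-specified one-sided Z-test. Report beside it the difference in ACP completion with a score-based interval such as Newcombe's. Use a 90% level if the interval is meant to agree with the one-sided 5% test. A 95% interval can conflict with it: an illustrative 6/8 versus 2/7 gives one-sided p = 0.036 with a 95% interval of −3 to +73 points.
4. Say that a non-significant result will not be read as no effect.
5. Date the change and mark it as made after closure to enrolment.

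The cost is a count of randomised dyads and some wording, with no new data and no change of test. The downsides are a less favourable stated power and an edit that comes after closure. The study is still active, so the correction can be made.

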### Number of subjects enrolled at Penn since the study was initiated

15

### Actual enrollment at participating centers

7

*If study is closed to further enrollment, please enter the following*

### Number of subjects in therapy or intervention

4

### Number of subjects in long-term follow-up only

0

## **IRB Determination**

If the change represents more than minimal risk to subjects, it must be reviewed and approved by the IRB at a convened meeting. For a modification to be considered more than minimal risk, the proposed change would increase the risk of discomfort or decrease benefit. The IRB must review and approve the proposed change at a convened meeting before the change can be implemented unless the change is necessary to eliminate an immediate hazard to the research participants. In the case of a change implemented to eliminate an immediate hazard to participants, the IRB will review the change to determine that it is consistent with ensuring the participant's continued welfare. Examples: Convened Board Increase in target enrollment for investigator initiated research or potential Phase I research Expanding inclusion or removing exclusion criteria where the new population may be at increased risk Revised risk information with active participants Minor risk revisions that may affect a subject's willingness to continue to participate Expedited Review Increase in target enrollment at Penn where overall enrollment target is not exceeded or potentially sponsored research Expanding inclusion or removing exclusion where the new population has the same expected risk as the previous, based on similarities of condition Revised risk information with subjects in long-term follow-up Minor risk revisions with no subjects enrolled to date

Expedited Review

## **Modification Summary**

Please describe any required modification to the protocol. If you are using this form to submit an exception or report a deviation, enter 'N/A' in the box below.

Dear IRB Administrator, We have outlined the changes below. Thank you for your attention. Personnel Changes Remove [name] as Study Contact Remove [name] as Study Contact Thank you!

## **Risk / Benefit**

Does this amendment alter the Risk/Benefit profile of the study?

No

## **Change in Consent**

Has there been a change in the consent documents?

No

**If YES, please choose from the options below regarding re-consenting**

## **Deviations**

**Are you reporting a deviation to this protocol?\***

No

## **Exceptions**

**Are you reporting an exception to this protocol?\***

No

# Protocol Details

## Resubmission\*

Yes

## Hospital Sites

Will any research activities and/or services be conducted at a Penn Medicine affiliated hospital site?

No

#### **Responsible Org (Department/School/Division):**

602 - Biobehavioral and Health Sciences

**Disclosure of Significant Financial Interests\***

Does any person who is responsible for the design, conduct, or reporting of this research protocol have a **FINANCIAL INTEREST**?

No

**Penn Intellectual Property\***

To the best of the Principal Investigator's knowledge, does this protocol involve the testing, development or evaluation of a drug, device, product, or other type of intellectual property (IP) that is owned by or assigned to the University of Pennsylvania?

No

**Certification**

I have reviewed the *Financial Disclosure and Presumptively Prohibited Conflicts for Faculty Participating in Clinical Trials* and the *Financial Disclosure Policy for Research and Sponsored Projects* with all persons who are responsible for the design, conduct, or reporting of this research; and all required Disclosures have been attached to this application.

Yes

## HRPP

**Human Source Material\***

Does this research include collection or use of human source material (i.e., human blood, blood products, tissues or body fluids)?

No

**Medical Information Disclosure\***

Does the research proposal involve the use and disclosure of research subject's medical information for research purposes?

No

**If the answer is YES, indicate which items is is provided with this submission:**

**CTRC Resources\***

Does the research involve CTRC resources?

No

**Pathology and Laboratory Medicine Resources\***

Will samples be collected by hospital phlebotomy and/or processed or analyzed by any of the clinical laboratories of the University of Pennsylvania Health System?

No

**Research Involves Apheresis, Cell Collection, and/or Blood Product Collection\***

Does this research involve collection of blood products in the Penn Donor Center and/or the use of apheresis for treatment or collection of cells or other blood components?

No

**Research involving blood transfusion or drug infusions\***

Will your research involve blood transfusion or infusion of study drug in 3 Ravdin Apheresis Unit for research purposes?

No

**Trial in Radiation Oncology**

Is this research a prospective trial being done in Radiation Oncology, and if so, has this protocol been approved by the Radiation Oncology Protocol committee?

N/A

**Study in Radiation Oncology**

Is this research a retrospective study being done in Radiation Oncology, and if so, has this project been reviewed by the Radiation Oncology Clinical Research Group?

N/A

**Use of UPHS services\***

Does your study require the use of University of Pennsylvania Health System (UPHS) services, tests or procedures\*, whether considered routine care or strictly for research purposes?

No

**Primary Focus\***

Sociobehavioral (i.e. observational or intervention)

**Protocol Interventions**

**Sociobehavioral (i.e. cognitive or behavioral therapy)**

**Drug**

**Device - therapeutic**

**Device - diagnostic (assessing a device for sensitivity or specificity in disease diagnosis)**

**Surgical**

**Diagnostic test/procedure (research-related diagnostic test or procedure)**

**Obtaining human tissue for basic research or biospecimen bank**

**Survey instrument**

**None of the above**

**The following documents are currently attached to this item:**

*There are no documents attached for this item.*

## ***Department budget code***

000 - 000 - 0 - 000000 - 0000 - 0000 - 0000

## ***Funding Sponsors***

### **Funding sponsors billing address**

If you have selected a commercial or industry sponsor, please provide the appropriate address and contact information for the Sponsor for the purposes of billing for IRB review fees (initial review, continuing review and convened modification fees apply here). If the Sponsor is not industry/commercial, this information is not necessary to provide with your application.

### **Funding sponsors gift**

Is this research being funded by a philanthropic gift?

### **Project Funding\***

Is this project funded by or associated with a grant or contract?

No

### **Sponsor Funding**

Is this study funded by an industry sponsor?

### **Status of contract**

### **The following documents are currently attached to this item:**

*There are no documents attached for this item.*

# Protocol

## ***Objectives***

### **Overall objectives**

One approach to decrease burdensome end-of-life transitions and treatments for PWD is to engage family decision-makers and, when possible, PWD, in advance care planning (ACP) conversations. These discussions should be documented and summarize the persons values, preferences for care, and treatment decisions in ways that facilitate communication with care providers. ACP is particularly important in dementia given the progressive nature of the disease that leads to gradual and irreversible loss of decision-making capacity. As a result, family caregivers are often called upon to make a variety of decisions related to care. Many PWD want to share in healthcare decision-making, but are often excluded from these conversations. Thus, resources to assist PWD and their family caregivers engage in ACP must use a shared decision-making approach that balances patient autonomy with declining capacity. Support for family caregivers also requires attention to the complexities of surrogate decision-making including: 1) ensuring that surrogate decision-makers (SDMs) decisions are informed by the

incapacitated persons values and preferences; 2) supporting SDMs in the common situation in which they did not have conversations about end-of-life care when the PWD was cognitively intact; and 3) attending to the uncertain legal status of formal advance directives completed by SDMs. Given that most PWD receive either short- or long-term care in a nursing home (NH) as their disease advances (described more fully in the Overall Research Plan), NH admission represents a critical opportunity for goals of care conversations and documentation of care preferences. Indeed, when these discussions occur, and PWD and SDMs are supported in articulating goals, most choose less aggressive approaches to care. Despite the opportunity for discussing treatment preferences, the NH admission process typically focuses only on decisions about cardiopulmonary resuscitation, although families of NH residents with advance dementia report that the most common care decisions they face involve feeding problems, infections and pain. Web-based ACP platforms facilitate completion of advance care plans, improve decision-making quality, and enhance shared decision making. However there are few studies that examine ACP in PWD, especially in the NH setting. Of the existing ACP platforms, most were developed for use with all older adults or those with advanced cancer or heart disease. Two recent randomized clinical trials examined the effects of dementia-specific ACP video decision aids; they showed increased rates of goals of care discussions and ACP completion. Although these results are promising, both investigative groups recommended integrating the decision aid into NH practice and more robust ACP programs. This pilot takes the first step in addressing these recommendations by adapting an existing successful online ACP platform to the specific needs of PWD and their SDMs. Moreover, the platform enables the development of written care plans that can be incorporated into the NHs electronic health record (EHR) and easily shared with caregivers and clinicians.

